### **2.10 Study adherence**

#### **2.10.1 Adherence tools**

In the screening phase (visit 1 to visit 2) Participants will be required to record home BP in the morning in triplicate in a seated position after 5 minutes rest and either reply to the reminder text message or transcribe into provided diary. In the intervention phase (visit 2 to visit 3), participants will be advised to take their dose of juice at the same time each day with food and continue to measure their BP in the morning. Participants will receive text messages with reminders to take BRJ and measure their BP. After 28 days of intervention, participants will be required to return to the clinic for a post-treatment assessment and biomarker collection. Adherence to the study protocol will be verified in real-time by reply to text messages or at Visit 3 by reviewing the participant diary. Patients will be encouraged to reply to the reminder message with their blood pressure readings as this will allow for monitoring of adherence in real-time. If participants chose not to reply to text messages, they will be contacted once per week via text message to ensure they do not have any unforeseen issues with the intervention.

#### **2.10.2 Text messaging management**

The management of the text message delivery will be by the MessageMedia web-based software program (Message Media, Victoria, Australia). The software program will allow a standard text message to be tailored and scheduled for delivery. The program will keep a log of all messages sent to each study participant and those which fail to be delivered. Data exports will be compliant with privacy legislation. There will be no access to these data by any third party, including the software developers.

During the screening period (unless participants opt out), participants will receive the following text message with their first name:

“Hi <First name>, this is your reminder to measure your blood pressure. Please respond to this message with your measurements in the order they were measured. Please also reply if any issues.”

During the intervention period (unless participants opt out), they will receive the following message:

“Hi <First name>, this is your reminder to consume your beetroot juice with food and measure your blood pressure. Please respond to this message with your measurements. Please also reply if any issues.”

#### **2.10.3 Adherence according to measurement recording**

Adherence will be assessed by the following;

- The time at which blood pressure measurements are received via MessageMedia will be considered as the time of BRJ ingestion (unless otherwise stated) and blood pressure measurements unless otherwise indicated by the participant; OR
- Evaluation of the participant diary (Appendix B) where the time of dose and blood pressure are recorded.

- Where participants miss a dose and associated blood pressure readings and alert study staff on the same day, they will be advised to consume BRJ with food and take blood pressure in triplicate as soon as possible on the same day.
- Where participants miss a dose and associated blood pressure readings and study staff are not alerted on the same day, participants will be advised to miss dose (i.e. not ‘catch up the dose’) and resume the usual protocol the following morning.
- Where participants do not respond to automated text messages for 2 consecutive days, study staff will contact them. Participants will be contacted by phone up to 3 times before they are considered lost to follow up. In

## 2.11 Study Schedule and Visits

### 2.11.1 Visit Schedule Overview

Refer to Appendix A: Schedule of Assessments

### 2.11.2 Visit Outlines

Study visits will occur at WIMR or at the renal department in WSLHD. If participants are unable to attend their visit due to unforeseen circumstances, the visit will be rescheduled as soon as possible. If Visit 3 is rescheduled, a protocol deviation will be filled in. Participants will be encouraged to attend follow up within 72 hours of their scheduled visit.

Details of each visit are described below.

#### Visit 1

The screening visit (Visit 1) will include:

- Study discussion, consent obtained, PICF signature and date
- Eligibility assessment: inclusion and exclusion criteria check
  - Taste test of nitrate depleted BRJ to ensure they can maintain the intervention (taste is identical to nitrate-rich BRJ)
- Collection of the following information/data:
  - Demographics
  - Family history of ADPKD
  - Medical history and ADPKD history
  - Prior and concomitant medication, over-the-counter medications, supplements
- Height, body weight and BMI
- Clinic blood pressure
- Blood sample collection
- Urine sample collection

- Saliva sample collection
- Provision of blood pressure monitor, associated instructions, blood pressure participant diary
- Randomisation
- Dispensing beetroot juice in sealed bag with clear instructions on bag not to open until after Visit 2

## Visit 2

Visit 2 will be held via phone and include:

- Eligibility assessment: inclusion and exclusion criteria check (including home blood pressure compliance/adherence based on text message response)
- Patient interview to collect the following data:
  - Confirmation of Visit 1 Medical/ADPKD history
  - Adverse Events
  - Medical history and ADPKD history since last visit
  - Changes to concomitant medications and supplements since last visit
- The investigator will also instruct the participant to open the sealed package to commence the BRJ the following day and continue to do daily home BP readings at the same time each morning

## Visit 3

Visit 3 will include:

- Collection of the following information/data:
  - Adverse Events
  - Medical history and ADPKD history since last visit
  - Changes to concomitant medications and supplements since last visit
- BP recording reconciliation and confirmation based on text message response (compliance/adherence)
- Clinic blood pressure
- Blood sample collection
- Urine sample collection
- Saliva sample collection
- Return of blood pressure monitor

### 2.12 Trial Procedures

#### 2.12.1 Blood pressure measurements

Clinic Blood Pressure: Clinic blood pressure will be taken at all visits. Blood pressure measurements will be taken in triplicate (1 minute between readings) in a seated position using a validated blood pressure monitor (oscillometric BP device: UA-651 A&D Medical, Tokyo, Japan) with an appropriately sized upper-arm cuff

after at least 5 minutes rest. In accordance with International Society of Hypertension 2020 guidelines and the 2018 European Society of Cardiology/European Society of Hypertension Guidelines,[51] an average of the second and third readings at each time-point will be taken for analysis.

**Home Blood Pressure:** Participants will be provided a validated blood pressure monitor (oscillometric BP device: UA-651 A&D Medical, Tokyo, Japan) with an appropriately sized upper-arm cuff and given training and instruction on taking measurements (Appendix C). At the screening visit, research staff will provide demonstration and training to the participants to ensure that they can obtain blood pressure readings at home. Participants will also be provided an information card with instructions. Participants will be required to consume oral dose of beetroot juice prior to record home blood pressure every morning upon waking. Blood pressures will be taken in triplicate (with 1 minute rest between readings) in a seated position after 5 minutes rest and recorded via text message reply or in the participant diary. As with the clinic blood pressures, an average of the second and third reading will be used for data analysis.

## **2.12.2 Sampling procedures**

**Blood:** At visit 1 and 3, after five minutes of rest (as plasma nitrate levels are affected by rapid changes in posture [52]), venous blood will be collected by venepuncture into one 8mL SST tube, which will immediately be centrifuged at 1000 x g (15 min at 4 °C) to separate the serum. The serum will be stored in aliquots and frozen at -30 °C until measurement. Serum samples will be used for measurement of NO metabolites (nitrate and nitrite) using a nitric oxide assay and asymmetric dimethylarginine ADMA (a NOS inhibitor and recognized marker of endothelial dysfunction) using ELISA.

To determine if patients fit the inclusion criteria at visit 1 (ie. Serum creatinine, absence of diabetes and uncontrolled hyperlipidemia), patients can provide results of a recent blood test or will have routine bloods performed.

**Urine:** Two urine samples will be collected at Visit 1 and 3. After participants return their urine collection bottles, one sample will be weighed and stored at -30 °C for measurement of NO metabolites (nitrate/nitrite and *N*-nitroso compounds), and the other sample will be sent for formal urine albumin to creatinine ratio measurement. The sample to be stored for *N*-nitroso measurement will be aliquoted and preserved in sodium hydroxide based on previous research that this improves the preservation of volatile *N*-nitroso compounds if any are present.[53]

**Saliva:** Whole saliva samples will be collected from participants at Visit 1 and 3 for genomic analysis of oral bacteria. Participants will be asked to rinse their mouths with bottled water at least 10 minutes prior. A spit saliva sample will be collected in sterile tube. Samples will then be aliquoted into 1.5mL Eppendorf tubes and stored at -80 °C.

## 2.13 Analysis of samples

### 2.13.1 Analysis of plasma and urine nitrate/nitrite by ELISA

Nitrate/nitrite analysis of plasma and urine will be performed using the commercially available colorimetric Nitric Oxide Assay Kit (ab65328, Abcam, Cambridge, U.K), based on the Griess assay, according to manufacturer's instructions. Briefly, nitrate is reduced to nitrite by the addition of nitrate reductase to the plasma and urine samples, followed by the addition of Griess reagent to form a deep purple azochromophore for measurement of nitrate/nitrite using a microplate reader (OD 540 nm).

### 2.13.2 Analysis of urine N-nitroso compounds by chemiluminescence

Urine analysis of *N*-nitrosamine and *N*-nitrosamide will be performed by chemiluminescence as described by Berends *et al.*[54]

### 2.13.3 Analysis of plasma asymmetric dimethylarginine (ADMA) by ELISA

Serum ADMA analysis will be performed using a commercially available quantitative sandwich enzyme-linked immunosorbent assay (ELISA) Kit (K7828, Immundiagnostik AG, Bensheim, Germany) according to manufacturer's instructions. Briefly, sample is added to a microplate coated with immobilised anti-ADMA antibodies to bind to ADMA present in the sample. Unbound substances are then removed followed by the addition of biotin conjugated ADMA specific antibodies. Between washes avidin conjugated Horseradish Peroxidase (HRP) is added. A substrate solution is then added developing a colour at an intensity proportional to the amount of ADMA in the samples.

### 2.13.4 Genomic analysis of oral bacteria from saliva samples

Saliva samples will be centrifuged at 15,000 x g for 10 minutes at 4 °C to separate the bacterial pellet. DNA will be extracted using the GenElute Bacterial DNA Extraction Kit (Sigma-Aldrich) according to manufacturer's instructions and modified for lysis. Oral microbiome profiling will then be performed by PCR gene amplification of 16S rRNA and pyrosequencing and analysed as described by Kapil *et al.* (2018).[55]

## 3 DATA MANAGEMENT

### 3.1 Data handling

Data will be collected on paper-based CRFs designed specifically for the study. Data will be kept confidential and each CRF have a unique participant identification number (ID) on each form. No participant names will appear in the forms. The CRF will be placed into a folder labelled with the participants' unique participant ID and will be stored in a secure location. All CRFs and relevant documentation will also be scanned to a secure server on the University of Sydney cloud system. Only the Principal Investigator and researchers will have access to documents linking participant personal information to Study ID code numbers, and this will be stored in a locked cabinet at WIMR and via password in the trial database.

The data management plan and electronic case report forms have been developed and harmonised using National Institutes of Health-Clinical Data Interchange Standards Consortium (NIH-CDISC) terminology for ADPKD to enable future data sharing if participants have provided extended consent. The data will be stored in a secure web-based platform and room at WSLHD and will be retained for a minimum of 15 years, as specified in the initial consent form.

### **3.2 Data Dissemination**

The results of the study will be disseminated at national and international Scientific Meetings and submitted for publication in leading peer-reviewed international journals, after the last participant has completed the final study visit and/or in the event of early termination of the trial for any reason. If the participants opted to receive the study results upon its completion, they will be contacted by email or message.

### **3.3 Publications**

The results of the clinical trial will be submitted to medical journals for publication by the Investigators. The results of the trial are the property of the Investigators, the Western Renal Service and Westmead Hospital.

## **4 SAFETY MONITORING AND REPORTING**

BRJ is a food supplement that is available for over-the counter consumption from commercial food outlets. Previous clinical trials have not reported any serious adverse effects.[19, 26] The trial staff will monitor for adverse effects at each study visit and review in at least fortnightly meeting between the Principal Investigator and Study Staff.

All serious adverse events will be reported immediately Lead Investigator and in turn to the WSLHD HREC but the Investigator will also note any trends in adverse events and report these also the WSLHD HREC. Initial reports of adverse effects will be followed by detailed written reports based on Case Report Forms (CRF). These CRF will identify the participant by their unique participant identifying number; the participant's name and medical record number will be removed. In the absence of a Data Safety Monitoring Board for this study, a flowchart (adapted from the University of Leicester, United Kingdom) will be used to guide unblinding (Figure 3). In the event of any premature unblinding (accidental unblinding or unblinding due to a serious adverse event) the Investigators will promptly document and report these events to the WSLHD HREC in accordance with ICH-GCP guidelines.

[figure not shown]

Figure 3: Flowchart to guide unblinding in the BEET-IT study (adapted from the University of Leicester, United Kingdom). SUSAR; suspected unexpected serious adverse event.

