### 2.2.2 Secondary Endpoints

The secondary outcomes assessing treatment efficacy in this study will be the change from baseline in the following:

- (a) mean daily home systolic and diastolic systolic and diastolic blood pressures
- (b) change in urinary albumin to creatinine ratio
- (c) levels of NO metabolites (nitrate and nitrite) in plasma and urine; and
- (d) plasma ADMA levels after dietary nitrate supplementation using BRJ.

To assess safety of chronic nitrate supplementation, the frequency and type of adverse events will be evaluated

To assess adherence to the study procedures, the following will be assessed:

- (a) Number/percent of completed/missed measurement of blood pressure as represented by response to automated text messages or completion of patient diary
- (b) Of measurements captured, number/percent of those who consumed BRJ and took measurements in morning period (6am-9am).

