## 2.4 Study Design

[figure not shown]
The total duration of the study is 35 days. Patients will be screened at Visit 1 and eligible patients will be provided with a blood pressure monitor (oscillometric BP device: UA-651, A&D Medical, Tokyo, Japan) to commence baseline home blood pressure monitoring for a 7 day run-in. Their compliance to daily blood pressure readings will be assessed via automated text message each morning (to which participants will reply with their readings), or with a phone call by study staff on Day 2 and 5 if they opt-out of text messages, and at Visit 2. Replying via text message will be encouraged as the preferred option as it will allow for real-time monitoring and data recording and allow patients to easily contact the study team if they have any issues. Participants will be randomly allocated nitrate-rich BRJ (400mg nitrate) or nitrate depleted BRJ (placebo) in a sealed bag and asked not to open it until instructed to do so after Visit 2.

At Visit 2 (conducted via phone), participants' home blood pressure records will be reviewed for compliance. Participants who have recorded  $<80\%$  of the daily blood pressure readings will be deemed non-compliant and excluded from the trial. Additional exclusion criteria assessed at Visit 2 includes eGFR, fasting lipid and glucose levels, use of antiseptic mouthwash (from V1 to V2 and willingness to comply for remainder of study). Any excluded participants will be asked to return all study equipment and the sealed bag of BRJ. Participants who meet all criteria will be asked to commence the intervention that they were allocated the following morning.

The intervention is BRJ commercially packaged BRJ in 70ml bottles. Participants will be instructed to drink one bottle per day (70ml) and measure their blood pressure at the same time every day. Participants will be asked to send their blood pressures via text or record it in their diary. A daily reminder text message will be sent, unless participants opt-out of this option.

After 28 days, participants will return for Visit 3 for post-treatment assessment and sample collection.

Blood and urine samples will be collected at Visit 1 and 3 for measurement of NO metabolites, ADMA levels and urinary albumin to creatinine ratio. A saliva sample will be collected at Visit 1 and 3 for future genomic analysis of oral bacteria.

**Figure 2.** Study design and participant timeline

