on an unaltered diet.[20] The reduction in clinic BP was 7.7/2.4mmHg (3.6-11.8/0.0-4.9,  $p<0.001$  and  $p=0.050$ ).[20] The home blood pressure measurements over the 4 weeks demonstrated an increasing magnitude of the effects with time; comparable with a standard dose of antihypertensive medication, with a reversal occurring only on washout. However, in contrast, in 2015, Bondonno *et al.* showed no effect on home and clinic blood pressure after 1 week of treatment with BRJ (2 x 70mL, 600mg nitrate; James White Beet-IT Shot) in individuals with high-normal blood pressure and treated hypertensives, despite parallel increased nitrate metabolism. This could be due to the relatively short duration of supplementation, and potential interference of multiple anti-hypertensive pharmacologic agents (2-3 per individual), low-nitrate diet, and/or extended time period between each dose.[49] Finally, in 2013, Gilchrist *et al.* observed no effect on blood pressure, macro or microvascular endothelial function after 2 weeks of BRJ (250mL, 450mg nitrate; James White Beet-IT) in hypertensive individuals with Type 2 diabetes mellitus. This was also potentially attributed to the relatively short duration of intervention, and the numerous biochemical perturbations associated with diabetes which leads to diminished vascular reactivity and impaired responsiveness NO.[33] Therefore for reproducibility and comparability, the current study will administer “Beet-IT Sport Shot” (70mL; James White Drinks, UK) containing ~400mg nitrate per dose for a duration of 4 weeks.[46]

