## APPENDIX A

### Schedule of Assessments

| Week                            | -1 (Screening and Run-in) |    |    |    |    |    |    | 1    |    |    |    |    |    |    | 2    |   |   |    |    |    |    |    |
|---------------------------------|---------------------------|----|----|----|----|----|----|------|----|----|----|----|----|----|------|---|---|----|----|----|----|----|
| Day                             | -7                        | -6 | -5 | -4 | -3 | -2 | -1 | 0    | 1  | 2  | 3  | 4  | 5  | 6  | 7    | 8 | 9 | 10 | 11 | 12 | 13 | 14 |
| Study visit              | X(1)                      |    |    |    |    |    |    | X(2) |    |    |    |    |    |    |      |   |   |    |    |    |    |    |
| Eligibility assessment   | X                         |    |    |    |    |    |    | X    |    |    |    |    |    |    |      |   |   |    |    |    |    |    |
| Informed consent         | X                         |    |    |    |    |    |    |      |    |    |    |    |    |    |      |   |   |    |    |    |    |    |
| Taste test BRJ           | X                         |    |    |    |    |    |    |      |    |    |    |    |    |    |      |   |   |    |    |    |    |    |
| Randomization            | X                         |    |    |    |    |    |    |      |    |    |    |    |    |    |      |   |   |    |    |    |    |    |
| Demographics             | X                         |    |    |    |    |    |    |      |    |    |    |    |    |    |      |   |   |    |    |    |    |    |
| Medical history          | X                         |    |    |    |    |    |    |      |    |    |    |    |    |    |      |   |   |    |    |    |    |    |
| Concomitant medications  | X                         |    |    |    |    |    |    | X    |    |    |    |    |    |    |      |   |   |    |    |    |    |    |
| Adverse events           |                           |    |    |    |    |    |    | X    |    |    |    |    |    |    |      |   |   |    |    |    |    |    |
| Vital Signs              | X                         |    |    |    |    |    |    | X    |    |    |    |    |    |    |      |   |   |    |    |    |    |    |
| Weight                   | X                         |    |    |    |    |    |    |      |    |    |    |    |    |    |      |   |   |    |    |    |    |    |

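### After the first dose, adverse events are systematically asked about only once, at Visit 3 (about Day 28), and the contacts in between are unstructured with no stated route into the adverse-event record

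*Combined protocol and SAP*

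**What the plan says.** Section 2.2.2 makes safety an outcome: "the frequency and type of adverse events will be evaluated". It gives no method of elicitation and no recall period.

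Section 4 sets the collection rule: "The trial staff will monitor for adverse effects at each study visit and review in at least fortnightly meeting". It also says that there is no Data Safety Monitoring Board, that serious events are reported at once, that the investigator notes trends, and that first reports are followed up in writing on case report forms.

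Section 2.11.2 lists adverse events at Visits 2 and 3 only. Visit 2 is a phone call at which staff "instruct the participant to open the sealed package to commence the BRJ the following day". Section 2.4 then says "After 28 days, participants will return for Visit 3 for post-treatment assessment and sample collection". In Appendix A, the row "Adverse events" is marked at Visit 2 and in the final column, and nowhere between.

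Other contact during treatment is described as follows:
- Section 2.10.2, the daily text unless the participant opts out: "Please respond to this message with your measurements. Please also reply if any issues".
- Section 2.10.1, for those who choose not to reply by text: "they will be contacted once per week via text message to ensure they do not have any unforeseen issues with the intervention".
- Section 2.10.3: staff make contact after two days without a reply, with up to three phone attempts before loss to follow-up is declared.
- Section 6.5.3: at consent, participants are asked to tell the team about symptoms straight away.

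The Appendix B diary has fields for dose time, measurement time and three blood pressure readings.

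**The concern.** The safety outcome is a count and a description of events, so it depends on how events are elicited. A single question covering four weeks is a weak instrument for short or mild complaints. The gastrointestinal symptoms that section 6.5.3 warns participants about are of that kind.

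The interim contacts could make up for this, but as written they yield no usable negative. A participant who sends readings and mentions nothing may have had no symptom, or may not have thought it counted as an issue.

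Two parts of the plan lean on information during exposure. The fortnightly meeting is the main ongoing oversight described in the absence of a monitoring board. Section 2.8.1 contemplates pausing and resuming the product for minor, reversible harms, which presupposes that such harms are noticed while the product is being taken.

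**Working it through.** The plan states no figure to reproduce. The check is a count on the study-day axis, followed by a comparison of the contact routes.

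**Inputs.** Visit 1 = Day −7 and Visit 2 = Day 0 (Appendix A); first dose = Day 1 (2.11.2); Visit 3 = Day 28 (2.4). Adverse-event items at Visits 2 and 3 (2.11.2, Appendix A). 60 participants, 35 days each, study activity May 2022 to April 2023 (Summary). Appendix A appears to mark juice from Day 0, whereas 2.11.2 says the day after the call. This may be only table layout, and it does not alter the conclusion.

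**1. Listed adverse-event questions.** They fall on Days 0 and 28. Number on Days 1 to 27: 0. Number after the first dose: 1.

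**2. Recall.** Time since the previous question: 28 − 0 = 28 days. An event starting on Day 1 is first asked about 28 − 1 = 27 days later. If Visit 3 slips by the 72 hours mentioned in 2.11.2, the interval is 28 + 3 = 31 days.

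**3. Interim routes.**

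| Route | Scheduled? | Asks about symptoms? | Stated path to the adverse-event record? |
|---|---|---|---|
| Daily text (2.10.2) | Yes | Open invitation only | No |
| Weekly text (2.10.1) | Yes, for those who do not reply | Problems with the intervention | No |
| Contact after two silent days (2.10.3) | Triggered by missing replies | Not stated | No |
| Report at once (6.5.3) | No, spontaneous | Yes | Section 4 sends first reports to a form; texts are not named |
| Serious events (4) | No, event-driven | Serious only | Yes |
| Diary (Appendix B) | Daily | No field | No |

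A participant on daily texts gets 28 prompts. A participant who opts out of them gets about 28 / 7 = 4 weekly contacts. The 28-to-4 contrast applies only to full opt-outs, whose number is unknown. Someone who stays on the daily text but does not answer still receives all 28, plus the weekly contact.

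**4. Fortnightly review.** Meetings within one participant's treatment: 28 / 14 = 2. The first has no visit-based on-treatment data for that participant; the second falls at about Visit 3. For the whole trial, assume even accrual of 60 participants over M months, with all completing. Visit 3 completions per fortnight are then 60 / [(30.4 × M − 35) / 14]:
- M = 10: 60 / (269 / 14) = 60 / 19.2 = 3.1
- M = 12: 60 / (329.8 / 14) = 60 / 23.6 = 2.5

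Treatment lasts two fortnights, so about 2 × 2.5 = 5 to 2 × 3.1 = 6 participants are on treatment at any meeting. Visit-based data come from the two or three who have just finished.

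**5. Participants who never reach Visit 3.** Section 2.9 withdraws anyone whose blood pressure medication is changed, and 2.10.3 defines loss to follow-up. The sample-size allowance in 2.6.1 is 30 − 28 = 2 per arm, or 4 of 60 (6.7%). No adverse-event question at withdrawal appears in the available text, in which the last item of 2.10.3 breaks off.

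**The case against.** The strongest reply is that the protocol keeps participants in close contact. Texts go out daily and invite reports of problems, section 2.4 encourages texting partly because it makes contact easy, silence triggers a call, symptoms are to be reported at once, and section 4 takes first reports on to a case report form. The product is an over-the-counter food for which section 1.1.5 describes minimal side effects. All of this stands, and it rules out several stronger readings that a reader might infer:

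- **That events are captured only at visits, or that no on-treatment information can arrive before Day 28.** The routes above contradict this. What is missing is a structured question and a stated path into the record.
- **That the fortnightly review is blind.** Enrolment is presumably staggered, so once the first participants finish, the meeting can see their Visit 3 data while others are still being treated.
- **That prompting differs seven-fold between those who reply by text and those who do not.** Receipt of the daily text depends on opting out, not on replying.
- **That the comparison between arms is biased.** Participants choose how they report, in a randomised, double-blind trial. Nothing links that choice to arm.
- **That follow-up after the last dose is needed because of rebound.** The remark in section 2.7.2, "with a reversal occurring only on washout", describes blood pressure lowering wearing off in an earlier study. It reports no adverse event.

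The reply does not remove the core point. An open invitation yields no recorded negative, the weekly text asks about the intervention and not about new symptoms, and the section 4 sentence on first reports does not say that a text counts as one.

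**Conclusion.** The point holds as a modest weakness in safety ascertainment. After the first dose there is one systematic adverse-event question, with a recall of about 28 days and none listed before it. Interim information is spontaneous and unstructured, and is not tied to the adverse-event record or the fortnightly review.

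The likely result is under-counting and uneven counting of mild or transient events in both arms. The documents give no recall or under-count rate, so that loss is not quantified. Participants who leave before Visit 3 (up to about 4 of 60 if drop-out matches the plan's own allowance and occurs during treatment) have no scheduled on-treatment question.

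The blood pressure endpoints and the reporting of serious events are unaffected. The conclusion assumes that no separate procedure already codes text replies as adverse events. If one exists, citing it would settle the recording part of the point, but not the lack of a structured question.

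**What to change.** 1. In section 2.10.2, replace the open invitation in the intervention-period text with a yes/no item on whether any new symptom has appeared since the last message.
2. Use the same item in the weekly text in section 2.10.1.
3. Add a symptom column to the Appendix B diary.
4. State in section 4 that each positive answer is entered on the adverse-event form with start and stop dates, and that the resulting log goes to the fortnightly review.

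This gives recorded negatives as well as positives, and leaves some on-treatment data for participants who do not reach Visit 3. It adds no visit and no new message.

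The cost is a wording change to automated texts and a printed form, submitted to the ethics committee if section 5.3 requires it. More minor events will be recorded in both arms, and existing staff will have slightly more follow-up. If participants have already been treated under the present wording, event counts before and after the change should be distinguishable in the report.
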